4. OBJECTIVE(S)/SPECIFIC AIMS AND HYPOTHESES

- *A concise statement of the goal(s) of the current study.*
- *The rationale for and specific objectives of the study.*
- *The goals and the hypothesis to be tested should be stated.*

1. To determine if IRIS facilitates interpretation of VLE images compared to VLE alone
2. To determine if IRIS increases the diagnostic yield for dysplasia compared to VLE alone and random biopsies
3. To determine if IRIS decreases the number of biopsies needed to identify dysplasia compared to VLE alone and random biopsies |

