10. ENDPOINTS

- *Describe the primary and secondary study endpoints*
- *Describe any primary or secondary safety endpoints*

The following outcomes will be measured:

- Primary Outcome: The time for image interpretation in each arm will be compared. Time will be a surrogate for ease of interpretation. Time will be recorded from start of image interpretation to the end of image interpretation. Length of Barrett's will be taken into account (time per cm of Barrett's) when comparing this outcome between patients and procedures.
- Secondary Outcome: Biopsy yield of dysplasia/diagnosis of dysplasia (dysplasia present versus not) of IRIS biopsies (double laser mark) will be compared to VLE without IRIS biopsies (single laser mark) and random biopsies.
- Secondary Outcome: The number of biopsies will be compared among all groups. |

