Both VLE and IRIS imaging are being performed as standard of care. However, randomization of the order allows for comparison of the two. Regions of interest (ROI) will be recorded using a full scan and recorded on the case report form. The time to identification of ROIs will also be recorded (from start of image interpretation to the end). Each group will then cross over such that the VLE without IRIS group will then have IRIS turned on ROI will then be recorded for each group based on full scans. A consensus ROI will be recorded based on the two exams. Only one ROI per centimeter will be allowed to avoid overlapping of laser marks. In addition VLE without IRIS and IRIS marks within 75 frames of each other or 2 hours (on a clock face orientation) will be considered the same target.

Laser marking will then be performed. A double laser mark will be applied to all IRIS ROIs. A single laser mark will be applied to VLE ROIs. Targeted biopsies will be taken of all laser marks and placed in separate biopsy jars. Biopsies will be taken in between the laser marks for double laser marked areas. For single laser marks, biopsies will be taken on either side of the laser mark. Resection of visible

lesions will then occur per standard of care (if present) followed by random biopsies of the segment. Random biopsies are pinch biopsies every 1 cm the length of the Barrett's in a 4 quadrant fashion per gastrointestinal society guidelines. This is all per standard of care. There are no additional research biopsies being performed outside this study. The targeted biopsies are based on the VLE features that are suspicious for dysplasia and thus standard of care. The other biopsies being performed here are random biopsies which are also being performed for standard of care. Biopsied samples will be stored per standard of care procedures per the pathology department. They will not be stored for future research purposes.

Following each procedure, the physician will be asked a series of Likert Scale questions to assess the utility of IRIS in that procedure, including how it impacts their confidence in image interpretation, their ability to assimilate data more easily and quickly, and their overall perception of the technology.

Although the VLE with IRIS and VLE without IRIS are being performed as standard of care, all adverse events will be recorded and reported to the IRB.

All data will be entered into a central encrypted REDCap database housed within the Northwell server.

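### The IRIS-versus-VLE biopsy count mixes targets found with a sampling rule that depends on mark type; the size and direction of the effect are unknown

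*Combined protocol and SAP*

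**What the plan says.** Section 11 (Research Procedures) ties the mark to the read that flagged the target: "A double laser mark will be applied to all IRIS ROIs", and "A single laser mark will be applied to VLE ROIs". It then ties the sampling to the mark: "Biopsies will be taken in between the laser marks for double laser marked areas", whereas "For single laser marks, biopsies will be taken on either side of the laser mark". Section 2 gives the same rules. Neither section states how many pieces are taken per target.

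Two further rules shape the counts. Nearby marks are merged into one target: "VLE without IRIS and IRIS marks within 75 frames of each other or 2 hours (on a clock face orientation) will be considered the same". The number of targets is also capped: "Only one ROI per centimeter will be allowed to avoid overlapping of laser marks".

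Section 10 (Endpoints) identifies IRIS biopsies by the double mark and VLE biopsies by the single mark. It adds a secondary outcome: "The number of biopsies will be compared among all groups". No unit (pieces, targets or jars) is given. The outcome serves the third aim in Section 4: "To determine if IRIS decreases the number of biopsies needed to identify dysplasia compared to VLE alone and random biopsies". Section 12 plans a two-group t-test for continuous variables, with medians or a log correction if the biopsy count is not normal. Nothing there standardises per target.

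**The concern.** The label being compared and the way tissue is taken coincide completely: every double-marked target is sampled one way and every single-marked target the other. A count of pieces by label is the product of two things: how many targets carry the label, which bears on what IRIS does, and how many pieces each such target receives, which follows from the sampling rule and local habit. Randomising the read order cannot separate them, because sampling follows the mark and not the order.

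At stake is the third aim. The trial could report that IRIS changes the number of biopsies when the two reads found equally many targets, or it could hide a real difference. Dysplasia yield per target has the same weakness, since a target sampled with more pieces has more chances of a positive result.

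**Working it through.** **1. The plan's own figure.** The only sample size stated is for interpretation time (Section 8): 94, or 47 per group. With a difference of 5 − 3 = 2 min, SD 3 min, two-sided alpha 0.05 and power 90%, n = 2 × [(1.960 + 1.282) × 3 / 2]² = 47.28 per group, which rounds up to 48, or 96 in total. (Section 8 labels both means as VLE without IRIS; one is taken here to be the IRIS mean.) The stated figure reproduces to within two patients. It says nothing about biopsy counts, for which the plan gives no calculation.

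**2. What a raw count measures.** For one patient, let *a* be targets found only on the IRIS read, *b* targets found only on the VLE read and *s* targets found on both. Let kI and kV be the pieces per double-marked and per single-marked target. Assume, as the marking rule suggests, that shared targets take the double mark. Then:

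- IRIS pieces = kI × (a + s)
- VLE pieces = kV × b
- ROIs found: a + s on the IRIS read, b + s on the VLE read

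The documents give none of kI, kV, a, b or s, so all values below are assumptions. With a = b = 1 the two reads find equally many ROIs, and every ratio (IRIS : VLE) ought to be 1.

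| Shared targets s | ROIs per read | Jars by mark type | Pieces, kI=1, kV=2 | Pieces, kI=2, kV=2 | Pieces, kI=3, kV=2 |
|---|---|---|---|---|---|
| 0 | 1 : 1 | 1 : 1 | 1 : 2 | 2 : 2 | 3 : 2 |
| 1 | 2 : 2 | 2 : 1 | 2 : 2 | 4 : 2 | 6 : 2 |
| 2 | 3 : 3 | 3 : 1 | 3 : 2 | 6 : 2 | 9 : 2 |

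The piece ratio falls on either side of 1 depending on quantities the plan leaves open. Counting jars by mark type removes kI and kV but keeps the shared-target effect. Only the ROI count per read stays equal in every row.

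**3. What a t-test would make of it.** Null data were simulated with equal Poisson target numbers under both labels, multiplied by assumed pieces per target, and compared by a two-sided two-sample t-test (4,000 runs per setting). This is the s = 0 row only. Shares of trials with P < .05, for a mean of 1 and of 2 targets per patient:

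| Pieces, IRIS vs VLE | 47 per label | 200 per label |
|---|---|---|
| 1 vs 2 | 88%, over 99% (VLE higher) | 100%, 100% |
| 2 vs 2 | about 5% | about 5% |
| 3 vs 2 | 46%, 77% (IRIS higher) | 98%, over 99% |

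**4. Yield per target.** If each piece has the same hit rate p and pieces are independent (both assumed), two pieces detect 1 − (1 − p)². For p = 0.2, 0.3 and 0.4 this gives 0.36, 0.51 and 0.64, against 0.20, 0.30 and 0.40 for one piece. Positive correlation between neighbouring pieces would narrow the gap.

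**5. The random comparator.** Its count is also set by rule: four quadrants every 1 cm, against at most one ROI per cm. A 4 cm segment gives about 4 × 4 = 16 random biopsies and at most 4 targets.

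**The case against.** A reader might infer that the protocol builds in a 2:1 excess of VLE biopsies and so a false result in favour of IRIS. The documents do not support that. Both sampling sentences speak of biopsies in the plural and give no number; they say where tissue is taken, not how much. Several pieces between two marks fits the text, and equal numbers per target would remove this part of the artefact. The shared-target rule works the other way: if both reads flag the same two sites, the count by mark type is two against zero in the direction of more IRIS biopsies. For the same reason the simulated rates in step 3 apply only when no targets are shared; they are not error rates for this design.

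It is also fair to say that Section 10 does not specify raw pieces, that the third aim speaks of biopsies needed to identify dysplasia and not of a bare count, and that the case report form and the flow diagram, which might define the count, are not available here. Section 8 expects little difference on the secondary outcomes in any case.

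What stands is this: in the text available, no unit is defined, no rule equalises pieces per target, the attribution of shared targets is not stated outright, and Section 12 corrects for none of these. The two influences may oppose each other, but nothing makes them cancel.

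**Conclusion.** The point holds in a limited form. Sampling differs by mark type, mark type is the comparison label, and pieces per target are not fixed, so a raw biopsy count can differ between IRIS and VLE with no difference in targets found. Neither size nor direction can be stated. The range of 1:2 through 1:1 to 3:2 without shared targets, and up to 9:2 with two shared targets per patient, rests wholly on assumed pieces per target and on shared targets taking the double mark. The count outcome and the per-target reading of dysplasia yield, both secondary, are affected. The primary outcome and the sample size are not.

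**What to change.** Amend Sections 10 and 12 and leave biopsy technique as it is.

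- **Count outcome, IRIS versus VLE:** the number of ROIs per patient recorded at each full scan before consensus merging, compared within patient by a paired method. A target found on both reads is credited to both. State whether the limit of one ROI per centimetre applies at each read or only to the consensus list.
- **Dysplasia yield:** compare per patient, crediting any dysplastic target to each read that found it. Shared targets then contribute equally to both reads, so unequal sampling can act only through targets found on one read.
- **Per-target yield:** if reported, show pieces per target by mark type beside it, and state that unequal pieces limit the comparison.
- **Random biopsies:** keep piece counts for a descriptive comparison.

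The cost is wording and a link from each jar to the read or reads that flagged it. Section 11 already has ROIs recorded from each full scan and targeted biopsies placed in separate jars. The drawback is that piece counts become descriptive for IRIS versus VLE. One limit remains: the second read follows the first in the same patient, so the ROI counts should also be shown by reading order.

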8. NUMBER OF SUBJECTS

- *Indicate the total number of subjects to be accrued locally. If applicable, distinguish between the number of subjects who are expected to be pre-screened, enrolled (consent obtained), randomized and complete the research procedures.*
- *If your study includes different cohorts, include the total number of subjects in each cohort.*
- *If this is multisite study, include total number of subjects across all sites.*

This is a multi-site randomized trial with an anticipated enrollment of 200 patients. We anticipate adding up to 3 other sites. Half of all patients should have a prior diagnosis of dysplasia to ensure a sample that has an adequate number of dysplastic patients.

The primary outcome will be time to interpretation of a VLE scan with and without IRIS. Dysplasia detected in each arm and number of biopsies are secondary outcomes and not expected to be that much different as expert VLE users will be involved in the study. The expected mean time for a VLE without IRIS is 5 min +/- 3 min. The mean time for a VLE without IRIS (standard) is 3 min. With a CI of 95% and power of 90%, the sample size for 1:1 randomization is 94 (47 in each group). Our sample size is 200 to allow for screen failures.

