12. STATISTICAL ANALYSIS

- *Describe how your data will be used to test the hypotheses.*
- *State clearly what variables will be tested and what statistical tests will be used.*
- *Include sample size calculations.*
- *If this is a pilot study, state which variables will be examined for hypothesis generation in later studies.*

The categorical variables will be compared using Fisher exact tests (eg: presence of dysplasia). Continuous variables between the two groups will be analyzed using the student t-test. All statistical tests will be 2-sided, and $P < .05$ will be considered significant. All statistics will be run using SAS version 9.4 (SAS Institute Inc, Cary, NC, USA).

Time to interpretation is likely normally distributed. For outcomes like number of biopsies, if post study analysis shows this is not normally distributed, we can use median values instead of means or perform a log correction.

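### Random biopsies come after resection of visible lesions, so the yield comparisons of IRIS and VLE with random biopsies are biased against random biopsies to an unknown degree

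*Combined protocol and SAP*

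**What the plan says.** Sections 2 and 11 describe the same fixed sequence. After laser marking, "Targeted biopsies will be taken of all laser marks and placed in separate biopsy jars". Resection of visible lesions comes next, and these "lesions will then occur per standard of care (if present) followed by random biopsies of the segment". The random scheme is systematic: "Random biopsies are pinch biopsies every 1 cm the length of the Barrett's in a 4 quadrant fashion per gastrointestinal society guidelines".

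Aim 2 in Section 4 is "To determine if IRIS increases the diagnostic yield for dysplasia compared to VLE alone and random biopsies". Section 10 makes this a secondary outcome: the yield of IRIS biopsies "will be compared to VLE without IRIS biopsies (single laser mark) and random biopsies". For the analysis, Section 12 says that "The categorical variables will be compared using Fisher exact tests (eg: presence of dysplasia" is the example given), and that "All statistical tests will be 2-sided", at the 5% level.

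No section keeps visible lesions out of the IRIS or VLE regions of interest, says to which method the histology of a resected lesion is credited, or limits the comparison with random biopsies to patients who had no resection.

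**The concern.** The methods do not sample the same tissue. Targeted biopsies sample the intact segment, and random biopsies sample what is left. If a dysplastic visible lesion lies inside an IRIS or VLE target, it can count as a targeted detection. Once it has been resected, it cannot count as a random one.

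This error runs in one direction only. A larger sample does not remove it. Randomising the order of IRIS and VLE does not help either, because random biopsies come last in both sequences. Part of any positive answer to Aim 2 against random biopsies could then reflect the sampling order rather than better targeting.

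**Working it through.** **The plan's own figure.** The only sample-size figure, in Section 8, concerns interpretation time. With a difference of 2 min (5 versus 3), SD 3, two-sided 5% and 90% power, n per group = 2 × [3 × (1.960 + 1.282) / 2]² = 47.3. This agrees with the stated 47 apart from rounding up. It has no bearing on yield, for which the documents state no sample size, prevalence, sensitivity or lesion rate.

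**Expected bias.** Let p be the share of patients with dysplasia present, s the sensitivity (the same for targeted and random sampling), and f the share of dysplastic patients whose detectable dysplasia is all removed before random sampling.

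- Targeted yield = p·s
- Random yield = p·s·(1 − f)
- Spurious gap = p·s·f, which is zero only if f = 0

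The assumed inputs are s = 0.5 and f = 0.10 to 0.30, with 100 or 50 dysplastic patients among the 200 planned (p = 0.50 or 0.25).

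- p = 0.50: targeted 25.0%; random 22.5%, 20.0% and 17.5% at f = 10%, 20% and 30%; gaps 2.5, 5.0 and 7.5 percentage points.
- p = 0.25: targeted 12.5%; random 11.25%, 10.0% and 8.75%; gaps 1.25, 2.5 and 3.75 points.

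**Chance of a false finding for targeted sampling.** I simulated 20,000 trials per row. Within a dysplastic patient, targeted and random detection were independent, and random detection was set to zero in a fraction f. The planned two-sided Fisher test compared the two yields, each out of 200. A trial was counted when p < 0.05 in favour of targeted sampling.

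| f | 100 dysplastic | 50 dysplastic |
|---|---|---|
| 0% | 0.6% | 0.3% |
| 5% | 1.6% | 0.6% |
| 10% | 3.5% | 1.1% |
| 20% | 15% | 4.8% |
| 30% | 39% | 13% |

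The rates at f = 0 fall below the nominal 2.5% in one direction because the Fisher test ignores that both yields come from the same patients. An exact McNemar test, which uses the pairing, gives about 2%, 8%, 25% and 52% at f = 0, 10, 20 and 30% with 100 dysplastic patients, and about 1%, 5%, 12% and 25% with 50. It is not the test in Section 12, so the Fisher figures describe the plan as written.

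**Which contrasts are affected.** IRIS and VLE targets are all biopsied before any resection, so their comparison with each other is untouched. Interpretation time is recorded before any tissue is taken.

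**The case against.** A reader might infer that the random comparator is stripped of dysplasia. The documents do not support that. Resection applies only to visible lesions, where there are any, in patients attending for surveillance (Section 7). Random biopsies still cover four quadrants of every centimetre, so flat dysplasia outside a resected lesion can still be found. Pinch biopsies of the targets remove little tissue. Depleted, in patients with a resection, is as far as the text goes.

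The size is also open to challenge. The documents give no value for f, and small values do little. Section 8 says "Half of all patients should have a prior diagnosis of dysplasia to ensure a sample that has an adequate number of dysplastic patients", but that concerns past diagnoses, so 100 patients with dysplasia detectable now is a generous case. A reader might also take the McNemar rates as the plan's error rates; they overstate what the planned test would do.

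Finally, this is an unpowered secondary outcome, and the order is described as standard of care. Both are true, and they limit how much weight the point carries. They do not answer it: the comparison with random biopsies is a stated aim, the direction of the bias follows from the order alone, and the analysis can address it without touching care.

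**Conclusion.** The point holds in a limited form. As written, the IRIS-versus-random and VLE-versus-random yield comparisons are biased against random biopsies whenever a dysplastic target lies in a lesion that is then resected.

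The direction rests on the text; the size rests on assumptions. With equal, independent 50% sensitivity and 10–30% of dysplastic patients fully depleted, a false result for targeted sampling arises in about 3.5–39% of trials (100 dysplastic patients) or 1–13% (50), against under 1% without depletion. If depletion is 5% or less, the effect is negligible. It would be wrong to conclude that the trial's main result, or the comparison of IRIS with VLE, is compromised.

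**What to change.** Add to Section 12:

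- The IRIS-versus-random and VLE-versus-random yield comparisons will also be made in patients with no visible lesion resected at the index procedure, and reported beside the all-patient result.
- Any claim of higher yield than random biopsies will rest on the two results agreeing, with the meaning of agreement stated in advance.
- The all-patient random result will be labelled as yield remaining after targeted sampling and resection.

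The order of biopsy and resection stays as it is.

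The cost is small. Resection status should be obtainable from the procedure and pathology reports that Section 20 says are kept. The price is fewer patients and a narrower population in one analysis of a secondary outcome; how many fewer cannot be said without a lesion rate. The added analysis also does not address the small amount of tissue removed by the targeted biopsies themselves.

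A reader might infer that the plan should go further, by making the resection-free set the main analysis or by dropping targets that lie inside a resected lesion. The first changes the question and sets aside patients who may be rich in dysplasia, so it is debatable. The second needs lesion position matched to the scan. Section 11 records regions of interest, but no section says that lesion position is recorded, so this would be new data capture rather than a wording change.

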12. STATISTICAL ANALYSIS

- *Describe how your data will be used to test the hypotheses.*
- *State clearly what variables will be tested and what statistical tests will be used.*
- *Include sample size calculations.*
- *If this is a pilot study, state which variables will be examined for hypothesis generation in later studies.*

The categorical variables will be compared using Fisher exact tests (eg: presence of dysplasia). Continuous variables between the two groups will be analyzed using the student t-test. All statistical tests will be 2-sided, and $P < .05$ will be considered significant. All statistics will be run using SAS version 9.4 (SAS Institute Inc, Cary, NC, USA).

Time to interpretation is likely normally distributed. For outcomes like number of biopsies, if post study analysis shows this is not normally distributed, we can use median values instead of means or perform a log correction.

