11. RESEARCH PROCEDURES

- *Include a detailed description of all procedures to be performed on the research subject and the schedule for each procedure.*
- *Include any screening procedures for eligibility and/or baseline diagnostic tests*
- *Include procedures being performed to monitor subjects for safety or minimize risks*
- *Include information about drug washout periods*
- *If drugs or biologics are being administered provide information on dosing and route of administration*
- *Clearly indicate which procedures are only being conducted for research purposes.*
- *If any specimens will be used for this research, explain whether they are being collected specifically for research purposes.*
- *Describe any source records that will be used to collect data about subjects*
- *Indicate the data to be collected, including long term follow-up*

This is a prospective randomized clinical trial examining how IRIS (Intelligent Real-time Image Segmentation) affects biopsy patterns in VLE (Volumetric laser endomicroscopy). Patients will undergo a VLE exam with and without IRIS per the standard of care. All patients regardless of the study participation in this study would receive VLE with and without IRIS clinically. Thus randomization into a particular order will not require more procedure time. They will be randomized into VLE without IRIS first vs VLE with IRIS first. Subjects will be randomized with the BUDDY Randomization System provided for use by the Northwell Health Biostatistics Unit. Randomization will occur before the procedure starts. Randomization will be stratified based on prior diagnosis of dysplasia. The order the patient is randomized to will be recorded on the case report form. There will be concealed allocation as the study coordinator performing the randomization will not know the order of the next allocation.

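### Dysplasia yield is compared between biopsy sources within the same patient, but section 12 assigns Fisher's exact test, names no paired or clustered method, and leaves the unit and the crediting of shared targets open

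*Combined protocol and SAP*

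**What the plan says.** Section 12 gives one rule for binary outcomes and names dysplasia as its example: "The categorical variables will be compared using Fisher exact tests (eg: presence of dysplasia". Continuous variables get a Student t-test between two groups, not labelled paired or unpaired. The only fallback, medians or a log correction, concerns the shape of the distribution.

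Section 10 defines the comparison as "Biopsy yield of dysplasia/diagnosis of dysplasia (dysplasia present versus not" and continues "of IRIS biopsies (double laser mark) will be compared to VLE without IRIS biopsies (single laser mark) and random biopsies". It adds, for counts: "The number of biopsies will be compared among all groups".

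Section 11 describes the sampling. Every patient has VLE both with and without IRIS, and "They will be randomized into VLE without IRIS first vs VLE with IRIS first". After both reads, all laser marks are biopsied into separate jars, and random four-quadrant biopsies follow in the same segment. On marking: "A double laser mark will be applied to all IRIS ROIs". VLE regions of interest get a single mark, and "For single laser marks, biopsies will be taken on either side of the laser mark". VLE marks and "IRIS marks within 75 frames of each other or 2 hours (on a clock face orientation) will be considered the same target".

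Section 8 refers to dysplasia detected per arm, calls it a secondary outcome, and expects little difference.

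**The concern.** The three biopsy sources named in section 10 are three measurements on one patient. Fisher's exact test treats them as three separate sets of patients. A patient with widespread dysplasia will tend to be positive on every source and a patient without dysplasia negative on all, so the results are probably positively correlated. The test ignores this.

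Two further gaps make the comparison hard to reproduce. The endpoint joins biopsy yield and diagnosis with a slash, so the unit could be the patient, the target or the biopsy. It is also unclear how a target found by both reads is counted. Section 10 identifies source by mark type, while section 11 double-marks every IRIS region and merges nearby marks. Read literally, a shared target is an IRIS target, and VLE keeps only what IRIS missed.

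Aims 2 and 3 in section 4 rest on these comparisons. Because little difference is expected, a non-significant result from an underpowered test could easily be read as showing that IRIS and VLE perform alike.

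**Working it through.** **The plan's own figure.** Section 8 gives 94 patients (47 per group) for interpretation time: means 5 and 3 minutes, SD 3, 90% power, two-sided 0.05. Per group, n = 2 × [(1.960 + 1.282) × 3 / 2]² = 47.28, so the figure reproduces to within rounding (96 in total if rounded up). It concerns time only. The documents give no dysplasia rate, overlap or correlation, so everything below rests on assumed inputs.

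**Patient as unit.** Assume 20% of patients positive on IRIS and 14% on VLE, with N = 200. The standard error that an independent-samples test implies for the difference is √[(0.20 × 0.80 + 0.14 × 0.86) / 200] = √(0.2804 / 200) = 3.74 points. The paired standard error is √[(p₁₀ + p₀₁ − 0.06²) / 200], where p₁₀ and p₀₁ are the proportions positive on one source only. Power is simulated at two-sided 0.05.

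| Both positive | IRIS only | VLE only | Correlation | Paired SE (points) | 6 / SE | Fisher power | Exact McNemar power |
|---|---|---|---|---|---|---|---|
| 13% | 7% | 1% | 0.73 | 1.95 | 3.07 | 17% | 85% |
| 10% | 10% | 4% | 0.52 | 2.61 | 2.30 | 24% | 55% |
| 7% | 13% | 7% | 0.30 | 3.13 | 1.91 | 28% | 42% |
| 2.8% | 17.2% | 11.2% | 0 | 3.74 | 1.60 | 31% | 31% |

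Fisher works with 3.74 points throughout, so it gains nothing as the true standard error falls.

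Under equal yields (20% on each source, N = 200), Fisher's actual error is 0.8% with 10% positive on both, 3.7% at independence (4% on both), 4.9% with 2%, 5.6% with 1% and about 6% with none. McNemar stays at 3.0% to 3.9%.

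**Target or biopsy as unit.** Assume 1.8 targets per source, 15% dysplastic in both sources, within-patient correlation 0.22, and 200 patients. Fisher's error is 4.4% if no target is shared, and 0.4% if 1.0 of the 1.8 is shared and credited to both sources. With two biopsies per target (within-target correlation 0.34) the two figures are 8.3% and 0.9%. With stronger within-target correlation (0.47) and no sharing it is 10.0%. A patient-clustered test stays near 5% in all these cases.

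**Crediting shared targets.** Keep the 1.8 targets per read, equal detection and 15% dysplastic, but count shared targets for IRIS only. With 1.0 shared, IRIS is credited with 1.8 targets per patient and VLE with 1.8 − 1.0 = 0.8. A difference is then declared in about 80% of trials of 200 patients (McNemar 83%, Fisher 78%). With 0.5 shared it is about 23% and 16%. Neither test corrects this.

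**Counts, only if the t-test is unpaired.** Assume means 2.0 and 1.6 in 94 patients. At correlation 0, 0.28 and 0.56, unpaired power is 53%, 53% and 55%; paired power is 53%, 66% and 86%.

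**The case against.** The best defence is that section 8 speaks of arms and section 12 of two groups, which would suit a comparison between randomized orders restricted to the first read. Fisher would be appropriate there. However, no such dysplasia analysis is described. Section 10 compares biopsy sources, each order arm supplies all three of them, and the random-biopsy contrast would still be within patient.

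A second defence is that a conservative test still controls false positives, and that these are secondary outcomes for which no power is claimed. This stands, and it limits the point. A reader might infer that the dysplasia p-values are generally invalid or biased towards false positives. The documents do not support that: at patient level the error exceeds 5% only if almost no patient is positive on both sources. Inflation to 8% to 10% needs biopsies as the unit, an assumed two per target (section 11 gives no number per mark) and no shared targets.

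A third objection is that changing the test achieves little while attribution is open. That is right, and in the scenarios above McNemar does slightly worse than Fisher. Attribution therefore has to be settled first.

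Finally, the widest gap (17% against 85%) needs a correlation of 0.73, and at independence the gap vanishes. No documented figure places the trial within that range.

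**Conclusion.** The concern holds. For dysplasia yield the plan names an independent-samples test for paired data, gives no paired or clustered alternative, and fixes neither the unit nor the crediting of shared targets. With the patient as unit and positive correlation, the harm is lost power: anything from none to 17% against 85% at assumed yields of 20% and 14% in 200 patients. With pooled biopsies the error can lie on either side of 5%, roughly 1% to 10%. All rates, overlaps and correlations are assumptions.

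The text should be corrected before results are seen, but the scope is limited. The outcomes are secondary, the stated sample size does not depend on them, and interpretation time is not part of this point.

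Two stronger readings should be avoided. One is that the t-test on biopsy counts is wrong as written: section 12 does not say it is unpaired, so this needs only clarification. The other is that comparisons with random biopsies should not be tested: aims 2 and 3 name them, and a paired method can handle them.

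**What to change.** In this order:

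1. Before results are seen, reconcile section 10 (source defined by mark type) with section 11 (all IRIS regions double-marked, nearby marks merged). For the analysis, credit a target found by both reads to both sources, using the regions recorded for each read.
2. Set the patient as the unit for dysplasia yield. Keep a patient with no target from a source in the analysis as negative for that source. Replace Fisher with exact McNemar, with IRIS against VLE as the main contrast. If targets or biopsies are also analysed, use GEE or a mixed model clustered on patient with reading order as a term.
3. Keep the contrasts with random biopsies and use the same paired method. Report with them that sampling density differs (four quadrants every 1 cm against at most one region of interest per cm) and that random biopsies follow targeted biopsies and any resection.
4. State in section 12 that the t-test for number of biopsies is paired, or use a count model with a patient effect.

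The cost is revised analysis wording and slightly more analysis work, with no new patients or procedures. The case report form must link each mark to the read or reads that found it. Section 11 already records regions for each read and uses separate jars.
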